STUDY PROTOCOL PLAN AND STADISTICAL ANALYSIS PLAN (SAP)

UNIVERSITY CEU CARDENAL HERRERA

Principal investigator: [name] [name]

TITLE: Second-generation Radiofrequency Application and Specific Therapeutic Exercise as a Treatment for Stress Urinary Incontinence Due to Urethral Instability. Randomised Clinical Trial

Research and Ethics Committee of CARDENAL HERRERA CEU UNIVERSITY:
CEEI25/646

NCT ID:

DATE: 01-14-2026

STUDY PROTOCOL PLAN

Objectives:

The objectives of our study have been the following:

The purpose of this study is to evaluate the correlation between urethral instability, assessed by ultrasound analysis of the bladder neck opening, and the severity of SUI, assessed by validated standard questionnaires. The determination of standard ultrasound parameters that allow urethral instability to be related to the severity of SUI would be a valuable finding for accurately diagnosing the severity of SUI using low-cost, easy-to-use imaging methods.

A randomized, single-blind clinical trial will be conducted in women with stress urinary incontinence (SUI). Participants will be randomly assigned to one of three intervention groups: radiofrequency (RF), specific pelvic floor muscle exercise (PFMT), or combined treatment (RF + PFMT). The study will be carried out at Clínica Traña (San José, Costa Rica), with an expected start date in 2025. The study will adhere to the principles of the Declaration of Helsinki and current European data protection regulations.

Adult women with urinary leakage and a bladder neck opening greater than 90°, assessed by functional ultrasound, will be included. Women with other pelvic floor disorders, pregnancy, recent treatments (RF, PFME, hormonal or laser therapies), relevant neurological, metabolic, or cardiovascular conditions, prior pelvic surgery, active infections, or contraindications to the interventions will be excluded. The estimated sample size is 117 participants (39 per group), calculated to detect statistically significant differences with 80% power and a 5% significance level, allowing for a 30% dropout rate.

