Before the intervention, all participants will undergo physical examination, digital palpation, and functional pelvic floor ultrasound, as well as complete validated questionnaires assessing urinary incontinence severity and quality of life (ICIQ-SF, King's Health Questionnaire, and Sandvik Severity Index). These assessments will be repeated at the end of the intervention and at 15 days, 3 months, 6 months, and 12 months post-intervention.

Randomization will be performed using statistical software, and outcome assessors will remain blinded to group allocation. Data will be coded and securely stored, ensuring participant confidentiality in accordance with the General Data Protection Regulation (EU 2016/679).

The RF intervention will consist of five weekly sessions of non-ablative fractional vaginal radiofrequency with temperature control and standardized parameters. The PFME program will comprise a structured core and pelvic floor exercise protocol supervised by physiotherapists, conducted twice weekly over a 16-week period. The combined group will receive both interventions.

Primary outcomes will include pelvic floor muscle strength and function (Oxford scale, endurance, and fatigability), ultrasound parameters (bladder neck opening, urethral hypermobility, and presence of prolapse), and validated questionnaires assessing urinary incontinence severity and quality of life.

Statistical Analysis Plan (SAP)

Data will be expressed as mean \pm standard deviation or as a percentage. The distribution of the sample will be determined using the Kolmogorov-Smirnov test. For quantitative variables, depending on the type of variable, Student's t-test or Mann-Whitney U test will be performed. The correlation between variables will be analyzed using Spearman's correlation. In the case of qualitative variables, the association between variables will be analyzed using bivariate or multivariate logistic regression, as appropriate, and contingency tables. The statistical significance of the difference between them will be evaluated using Pearson's χ^2 test. Statistical significance will be assumed with p-values <0.05 .

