To evaluate the diagnostic capacity of bladder neck opening measured by ultrasound analysis in the classification of the severity of stress urinary incontinence, a logistic regression analysis was performed. The dichotomized severity of the Sandvick test (mild/moderate versus severe/very severe) will be taken as the gold standard. Demographic and clinical variables will be evaluated as possible covariates and included in subsequent models if they had a p-value < 0.200 .

Sensitivity, specificity, Youden's index (sensitivity + specificity - 1), and positive and negative likelihood ratios (LR+ and LR-) will be calculated for bladder neck opening at rest, during the Valsalva maneuver, the variation between the two, and for the maximum model with the three variables.

The optimal cutoff point for bladder neck opening at rest will be determined using the Youden index. Subsequently, this value will be transformed into clinical units (mm) by algebraic solving of the logistic model equation, adjusted for relevant covariates (age and BMI). This approach preserves the statistical fit of the model while providing a clinically interpretable threshold.

Studentized residuals, leverage values, and Cook's distances will be estimated to identify possible outliers and influential values in the dependent variable, the predictors, and the model as a whole.

Receiver operating characteristic (ROC) curves will be constructed to determine the area under the curve (AUC). Likewise, the Hosmer-Lemeshow goodness-of-fit test will be applied to compare the observed and expected frequencies of the model (considering $p > 0.05$ as an adequate fit). The accuracy of the probabilistic predictions will be evaluated using the Brier Score (lower values indicate better performance). The

analysis will be performed using SPSS Statistics 29.0 (IBM Corp.)

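### The SAP names no method for ordered categories: if Sandvik class and Oxford grade are tested as qualitative variables, Pearson's chi-square ignores their order and may cost roughly 5 to 30 points of power

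*Combined protocol and SAP*

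**What the plan says.** All the general test choices stand in the first paragraph of the Statistical Analysis Plan (SAP).

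- Qualitative variables: "In the case of qualitative variables, the association between variables will be analyzed using bivariate or multivariate logistic regression, as appropriate, and contingency tables". The next sentence adds: "The statistical significance of the difference between them will be evaluated using Pearson", that is, Pearson's chi-square test.
- Quantitative variables: "For quantitative variables, depending on the type of variable, Student", followed by the t-test with Mann-Whitney U as the alternative.

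No ordinal model, trend test, three-group rank test, exact test or rule for sparse tables appears anywhere in the SAP. The paragraph does not list which outcomes are qualitative and which are quantitative.

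The Study Protocol Plan names the Oxford scale and the validated severity questionnaires among the primary outcomes, and the Sandvik index is one of those questionnaires. The SAP describes the use of Sandvik only once, in the diagnostic-capacity paragraph, as four named classes cut into two: "The dichotomized severity of the Sandvick test (mild/moderate versus severe/very severe".

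On size, the Study Protocol Plan states "The estimated sample size is 117 participants (39 per group", with a "5% significance level, allowing for a 30% dropout rate".

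**The concern.** Sandvik class and Oxford grade are ordered. A treatment that works should move women along the scale, from severe towards milder or from weak towards strong. Pearson's test gives the same result if the classes are shuffled, so it is not aimed at such a shift. It spreads its power over every possible pattern of difference between arms.

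The plan leaves open whether these outcomes go to that test. If they do, a real shift in a primary outcome could be missed although the collected data show it. If the assignment stays open, the choice between a chi-square and a rank test can be made after the data are seen.

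**Working it through.** **1. Completers per arm.** From the Study Protocol Plan: 39 per arm, 30% dropout.
39 × (1 − 0.30) = 27.3, so about 27.
In reverse, 27 / 0.70 = 38.6, rounded up to 39, which reproduces the plan's figure. (30 × 1.3 = 39 fits too, so the plan's own number before dropout is uncertain; a 30% loss from 39 still leaves about 27.)
The claim "calculated to detect statistically significant differences with 80% power" cannot be reproduced, because no outcome, effect size or test is given. For scale, 27 per arm gives 80% power for a standardised difference of 0.78 in a two-sided 5% t-test.

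**2. Why order matters.** Pearson's statistic is Σ(O − E)²/E over all cells, which does not change when classes are permuted. Its degrees of freedom are (arms − 1) × (classes − 1):
- two arms: 3 for four classes, 5 for six grades;
- three arms: 6 for four classes, 10 for six grades.

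Mann-Whitney uses 1 and Kruskal-Wallis across three arms uses 2, whatever the number of classes.

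**3. Power comparison.** Inputs that the documents do not give, and which are therefore assumptions:
- two-sided 5% tests;
- four-class mixes in percent of 25/25/25/25, 15/35/35/15, 10/40/35/15 and 5/25/45/25;
- six Oxford grades, with one equal and one bell-shaped mix;
- a proportional-odds shift, meaning the same log odds ratio at every cut between classes.

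There were 20,000 simulated tables per scenario with 27 per arm. The rank tests were corrected for ties. Log odds ratios of 0.7, 1.33 and 2.1 are odds ratios of about 2.0, 3.8 and 8.2.

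| Comparison | Log OR | Pearson | Rank test | Gap (points) |
|---|---|---|---|---|
| Two arms, four classes | 0.7 | 16.4–18.8% | 27.2–28.6% | 9.8–10.8 |
| | 1.33 | 53.1–57.1% | 72.4–74.7% | 17.6–19.3 |
| | 2.1 | 92.4–93.1% | 97.9–98.1% | 4.9–5.5 |
| Two arms, six grades | 0.7 | 12.4–15.1% | 29.3–30.5% | 15.4–16.9 |
| | 1.33 | 45.7–47.9% | 75.8–76.1% | 28.2–30.1 |
| | 2.1 | 89.3–89.4% | 98.6% | 9.2–9.3 |
| Three arms, four classes | 0, 0, 1.33 | 55.1–58.3% | 75.2–77.7% | 19.3–20.3 |
| Three arms, six grades | 0, 0, 1.33 | 47.0–50.4% | 79.0–79.8% | 29.4–31.9 |

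Over all effects tried, the two-arm gap was 5 to 19 points for four classes and 9 to 30 for six grades. The three-arm gap was 15 to 21 and 25 to 32. With three equal classes it was 3 to 9 points for two arms and 10 to 12 for three.

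**4. Yes/no outcomes.** A 2×2 table has no order to lose. The tie-corrected rank statistic equals Pearson's times (N − 1)/N, here 53/54 = 0.98, so the gap is essentially zero.

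**5. Low expected counts.** With equal arms of 27, a class reaches an expected count of 5 only if its pooled share is at least 5/27 = 18.5%. The share of two-arm tables with at least one expected count below 5 was:
- four equal classes with no effect: 38%;
- the uneven four-class mixes: 90 to 99%;
- six grades: essentially 100%.

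With no effect, over the two- and three-arm scenarios, Pearson's test rejected in 3.9 to 5.1% of tables and the rank tests in 4.6 to 5.3%. Sparse cells therefore did not inflate type I error. The gap in step 3 comes from ignoring order.

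**The case against.** The strongest objection is that the SAP never sends Sandvik class or Oxford grade to Pearson's chi-square. Mann-Whitney stands in the same paragraph, and an index and a graded scale can naturally be read as scores that belong there. On that reading a two-arm comparison loses nothing, because Mann-Whitney is the remedy itself. The diagnostic paragraph does not settle the matter: it uses Sandvik, cut in two, as a reference standard and not as an outcome compared between arms. This objection stands, and it makes the loss conditional. It does not close the gap in the plan. Mann-Whitney is written for quantitative variables, no sentence places either outcome there, and it compares two groups while the trial has three. Logistic regression is also listed, but not as an ordinal model.

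The second objection is that the figures rest on assumed class mixes, effects and number of grades. In addition, every scenario was a proportional-odds shift, the alternative that favours rank tests. That stands too. Differences that do not run in one direction would narrow or reverse the gap.

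Third, a reader might infer that low expected counts make the chi-square invalid here or explain the lost power. The results do not support either inference: the error rate held with sparse tables.

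**Conclusion.** The point holds as a conditional one. The SAP names no method for ordered categories and does not say how two ordered outcomes are classed. If they are treated as qualitative, the stated test discards their order. At about 27 completers per arm, the cost is then roughly 5 to 20 points of power for four classes and 10 to 30 for six grades. It is largest at moderate effects and small where both tests are close to full power. These figures depend on the assumed mixes, on six Oxford grades, on proportional odds and on the full 30% dropout.

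Two stronger readings are tempting. One is that the plan tests every categorical outcome, Sandvik and Oxford included, with chi-square. The documents leave that assignment unstated, and they also list Mann-Whitney and logistic regression. The other is that a fixed loss of 15 to 30 points follows for categorical outcomes in general. The documents give no class shares or effects from which to derive such a figure, and yes/no outcomes, such as whether prolapse is present, lose nothing.

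**What to change.** State in the SAP that Sandvik class and Oxford grade are compared between arms as ordered outcomes:

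- across the three arms, by Kruskal-Wallis or by proportional-odds regression with arm as a factor;
- for pairs of arms, by Mann-Whitney.

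Keep Pearson's chi-square for binary or unordered variables. Naming an exact test for sparse tables is optional good practice; the results above show no harm that it would cure.

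The cost is a few sentences: no new data, no extra participants, and the methods can be run in the software already named. The one downside is that the regression version assumes a roughly common odds ratio across classes.

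### The SAP gives two unreconciled covariate rules for the diagnostic model (a p<0.200 screen, and age and BMI) and no internal validation, so the millimetre cut-off may be undefined and adjusted-model performance is likely to be flattered

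*Combined protocol and SAP*

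**What the plan says.** The first aim under Objectives is to relate bladder neck opening on ultrasound to the severity of stress incontinence. The SAP serves it with a logistic regression on a binary outcome: "The dichotomized severity of the Sandvick test (mild/moderate versus severe/very severe) will be taken as the gold standard". The expected share of severe or very severe cases is not given.

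- **Covariates, in the paragraph on diagnostic capacity:** demographic and clinical variables are candidates, to be "included in subsequent models if they had a p-value < 0.200". The candidates are neither named nor counted, and the text does not say whether the p-value comes from a univariable or a multivariable model.
- **Cut-off, two paragraphs later:** "The optimal cutoff point for bladder neck opening at rest will be determined using the Youden index". It is then turned into millimetres by solving the logistic equation, "adjusted for relevant covariates (age and BMI". The plan does not say whether these two are set in advance or are what the screen is expected to leave.
- **Performance:** sensitivity, specificity, Youden index and likelihood ratios are planned for three single ultrasound measures and "for the maximum model with the three variables". In addition, "Receiver operating characteristic (ROC) curves will be constructed to determine the area under the curve (AUC", with a Hosmer-Lemeshow test and a Brier score. No bootstrap, cross-validation, shrinkage or validation sample is described.
- **Sample:** "The estimated sample size is 117 participants (39 per group". This number is not linked to the diagnostic analysis.

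**The concern.** A screen lets the data choose the covariates; the cut-off paragraph names them. The millimetre threshold comes from solving an equation, so it needs one known set of terms. Two analysts who follow the text faithfully could solve different equations and report different thresholds.

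There is also a question of honesty of performance. When covariates are selected, coefficients fitted, a cut-off optimised and discrimination measured all in the same women, the reported figures describe that sample better than they describe new patients. Hosmer-Lemeshow and Brier statistics computed on the development data do not correct for this. A usable ultrasound threshold is a main product of the study, so its definition and its stated accuracy both matter. The randomised comparison is not touched.

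**Working it through.** **1. The plan's own number.** 3 × 39 = 117. With 30% dropout, 27/(1 − 0.30) = 38.6, rounded up to 39, so 117 fits 27 evaluable women per group, or 3 × 27 = 81 (30 × 1.3 = 39 also fits). The base figure cannot be reproduced, because no effect size or SD is given. The visit used for the diagnostic model is not stated, so N = 117 and N = 81 serve as brackets.

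**2. The equation to be solved.** With opening, age and BMI in the model, the opening at a chosen probability p\* is

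opening\* = [logit(p\*) − b0 − b2·age − b3·BMI] / b1.

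If age fails the screen there is no b2. If a further variable x4 passes, a term b4·x4 appears that the cut-off paragraph does not mention. The plan covers neither case.

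**3. How often the screen admits unrelated variables.** For k independent unrelated candidates, P(at least one passes) = 1 − (1 − 0.20)^k:

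- k = 5: 1 − 0.8^5 = 67%, 1 expected
- k = 10: 1 − 0.8^10 = 89%, 2 expected
- k = 20: 1 − 0.8^20 = 99%, 4 expected

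**4. Events per parameter** (N × severe share / parameters; the shares are assumed):

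- Opening + age + BMI: from 81 × 0.20/3 = 5.4 to 117 × 0.50/3 = 19.5
- Eight parameters: from 81 × 0.20/8 = 2.0 to 117 × 0.50/8 = 7.3

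**5. Simulation.** All of these inputs are assumptions, not taken from the documents: independent standard-normal predictors; log-odds per SD of 0.8 for opening and 0.3 each for age and BMI; severe share 20%, 35% or 50%; 5, 10 or 20 candidates, counting age and BMI, with the rest unrelated to severity; univariable screening. Each scenario had 300 runs and 10,000 new women for testing. Optimism is apparent minus new-data value; the table gives the range of scenario means.

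| Model | AUC optimism, N=117 | AUC optimism, N=81 | Youden optimism, N=117 | Youden optimism, N=81 |
|---|---|---|---|---|
| Opening alone | −0.016 to 0.007 | −0.012 to 0.007 | 0.074 to 0.126 | 0.091 to 0.146 |
| Age and BMI fixed | 0.015 to 0.037 | 0.031 to 0.053 | 0.102 to 0.160 | 0.145 to 0.208 |
| Screened at p<0.200 | 0.042 to 0.157 | 0.063 to 0.211 | 0.143 to 0.339 | 0.189 to 0.441 |

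At N=117 the excess of screening over fixed covariates runs from 0.042 − 0.023 = 0.019 (35% severe, 5 candidates) to 0.157 − 0.034 = 0.123 (20% severe, 20 candidates). Age and BMI both passed the screen in only 13% to 30% of runs across all scenarios.

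**6. Calibration.** This was checked in a different assumed scenario: 117 women, 30% severe, 8 unrelated candidates, log-odds per SD of 0.6 for opening and 0.35 each for age and BMI, two separate sets of 600 simulated trials.

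- Screened: apparent AUC 0.74 to 0.75 against 0.65 in new data; median calibration slope 0.55 to 0.56.
- Fixed: 0.72 against 0.68 to 0.69; slope 0.81 to 0.82.

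A milder case (50% severe, 5 unrelated candidates) gave 0.72 against 0.66 with slope 0.67 when screened, and 0.71 against 0.69 with slope 0.83 when fixed.

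**The case against.** **The two sentences can be read together.** A reader might infer that they flatly contradict each other. The plan never says age and BMI are fixed. Calling them relevant can mean that they are expected to pass the screen, or did pass it, and the past tense in that part of the SAP leaves the second reading open. Both sentences hold if age and BMI pass and nothing else does. That stands: this is an unresolved ambiguity, not a proven contradiction. It still leaves every other outcome of the screen uncovered.

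**The size is not in the documents.** A reader might infer that the model is certain to be overfitted and to fail in new patients. The candidate count, severe share and effect sizes are all assumed, and at the low end the extra optimism is small. The simulation also makes age and BMI true predictors and all other candidates noise, which favours the fixed model. So the direction is likely, while the size is only illustrative.

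**Not every metric is affected.** It is tempting to extend the point to all reported accuracy. The screen cannot change the AUC of a single unadjusted ultrasound measure, and the three-variable model is not described as containing screened covariates. Nor is a millimetre value itself optimistic. It can be unstable, and the sensitivity, specificity and Youden index attached to it can be optimistic. Much of that comes from maximising Youden on the same data, which occurs even with opening alone.

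**Removing the screen is not the only remedy.** Listing the candidates and repeating the screen inside a bootstrap would also give honest performance figures. That is a fair alternative, but it would not by itself say which equation yields the threshold.

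**Conclusion.** The point holds as an unreconciled covariate rule combined with missing internal validation. As written, the equation behind the millimetre threshold is defined only if the screen happens to return exactly age and BMI. For the covariate-adjusted models, AUC and calibration are likely to look better than they are. Fixing the covariates removes much of the AUC optimism but not all of it, and it does not cure the optimism from choosing the cut-off on the same women. These magnitudes rest on the assumed candidate counts, severe shares and effects set out above. The sample of 117 was not derived for this analysis and neither supports nor refutes them. The matter should be corrected before analysis; it bears on the diagnostic claim only.

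**What to change.** In the SAP:

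1. Delete the p<0.200 screen. State that the covariate-adjusted models, including the one used for the millimetre conversion, adjust for age and BMI whatever their p-values. Leave the planned unadjusted single-measure analyses as they are.
2. Report bootstrap optimism-corrected AUC, calibration slope, sensitivity, specificity and Youden index, repeating the cut-off selection in every bootstrap sample.
3. Give a bootstrap interval for the millimetre threshold.
4. If the sponsor keeps a screen, list the candidates in advance, say how the p-value is obtained and which equation is solved when age or BMI fails or another variable passes, and repeat the screen in every bootstrap sample.

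The cost is SAP wording and a bootstrap run, with no new patients or visits. The reported performance may be somewhat lower.

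### Does the combined bladder neck model fail because its third variable is computed from the other two?

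*Combined protocol and SAP*

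**What the plan says.** The diagnostic part of the Statistical Analysis Plan (SAP) section uses logistic regression to relate bladder neck opening to severity of incontinence. The outcome is binary: "The dichotomized severity of the Sandvick test (mild/moderate versus severe/very severe) will be taken as the gold standard". Both likelihood ratios, Youden's index, and the sensitivity and specificity behind it are planned for "bladder neck opening at rest, during the Valsalva maneuver, the variation between the two, and for the maximum model with the three variables".

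The section gives no formula or unit for "the variation between the two". It also plans ROC curves with AUC, the Hosmer-Lemeshow test, residual and influence diagnostics, and a Brier score ("The accuracy of the probabilistic predictions will be evaluated using the Brier Score"). Demographic and clinical covariates are to be "included in subsequent models if they had a p-value < 0.200"; that rule does not cover the ultrasound terms. The cut-off for opening at rest is converted to mm through the logistic equation, with age and BMI as the only adjustment named.

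The section's general paragraph sets 0.05 as the threshold for significance. The diagnostic part does not say that odds ratios or p-values of individual ultrasound terms in the combined model will be reported or interpreted.

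**The concern.** The natural reading of the variation is Valsalva minus rest. The third variable is then an exact linear function of the first two. A logistic model with all three and an intercept has no unique coefficients, so one term has to be left out, and the plan does not say which.

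This could matter because relating bladder neck opening to severity is a stated purpose of the study, and this is the fullest model for it. If odds ratios were shown, whether rest or Valsalva looked independently associated with severity could turn on an unrecorded choice. A reader might also credit the model with three sources of information when it has two.

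**Working it through.** **Inputs.** From the SAP section: the three predictors, the binary outcome and the list of outputs. From the Objectives: 117 participants, used only as the size of the simulated data sets. The plan states no figure for this model, so there is none to reproduce. The documents give no distribution for the openings, so the numerical example rests on assumptions: rest R with mean 100 and SD 10, difference D with mean 25 and SD 10, Valsalva V = R + D.

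**Step 1: rank.** With D = V − R, the design matrix [1, R, V, D] has rank 3 of 4. This is algebra and holds at any sample size; three simulated data sets confirmed it.

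**Step 2: what each two-term version estimates.** Write the model without D as a + b1·R + b2·V.
- Leave out V, using V = R + D: a + (b1 + b2)·R + b2·D.
- Leave out R, using R = V − D: a + (b1 + b2)·V − b1·D.

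These are one model in three notations. The intercept and any covariate coefficients are the same in each, so covariate p-values and the overall likelihood-ratio test do not depend on the choice.

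**Step 3: one simulated data set** (53 severe cases among 117), coefficient and p-value:

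| Term left out | Rest | Valsalva | Difference |
|---|---|---|---|
| Difference | 0.04048 (0.19) | 0.01106 (0.57) | – |
| Valsalva | 0.05154 (0.030) | – | 0.01106 (0.57) |
| Rest | – | 0.05154 (0.030) | −0.04048 (0.19) |

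The entries follow Step 2: 0.04048 + 0.01106 = 0.05154.

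**Step 4: the planned outputs in the same data set.** All three versions gave log-likelihood −77.8476, AUC 0.608 and Brier score 0.2368. At the Youden point, sensitivity was 0.7547 and specificity 0.4375, so:
- Youden's index = 0.7547 + 0.4375 − 1 = 0.1922
- LR+ = 0.7547 / (1 − 0.4375) = 1.34
- LR− = (1 − 0.7547) / 0.4375 = 0.56

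Hosmer-Lemeshow uses only the fitted probabilities and outcomes, so it is unchanged too. In a separate simulated data set the largest gaps between versions were 3e-16 for fitted probabilities, 7e-13 for leverage and 3e-13 for Cook's distance, which is rounding error.

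**Step 5: other readings.** If the variation is percent change, 100·(V − R)/R, the rank is 4 of 4 and the model can be fitted as written. Collinearity may be strong: variance inflation factors ran from about 66 to 272 under the assumptions above, and the median for the worst term from about 4 to 196 under other assumed distributions. That widens the standard errors of single coefficients but leaves one well-defined set of fitted probabilities. An absolute difference is exactly collinear only if no woman has Valsalva below rest.

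**The case for a change.** The strongest reply is that a model named by three terms that cannot be fitted with three terms is wrongly specified, whatever is reported from it. Nothing else in the section resolves it: the covariate rule does not apply to these terms, and influence diagnostics do not reveal collinearity. The general paragraph uses logistic regression for association and judges p-values at 0.05, so odds ratios may well be shown. In simulations under five assumed scenarios, with 2,000 data sets each, the 0.05 verdict on rest changed with the omitted term in 46% to 79% of data sets and its sign in 30% to 94%. A sentence would settle the matter.

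Part of this stands. The variation is undefined and, on the difference reading, the label overstates the number of predictors. The percentages, however, are not error rates. They compare b1 (rest with Valsalva held fixed) with b1 + b2 (rest with the difference held fixed). These answer different questions and may properly differ in sign and significance in any such data. The rates also depend wholly on assumed distributions and effects. The 0.05 threshold is general and does not commit the authors to interpreting single ultrasound terms here. Nor is the derivation hidden, since the sentence itself presents the third variable as a comparison of the other two.

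**Conclusion.** The algebra is right and the consequence for the plan is nil. On the difference reading, the combined model is a two-predictor model under a three-variable name, and every accuracy, calibration and influence measure planned for it is the same whichever term is left out. On the percent-change reading the exact collinearity does not arise. An analyst will meet the redundancy when fitting the model and will have to state how the variation was computed to report its own single-variable result. A prior definition would tidy the wording without changing a planned result of the combined model on the difference reading.

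This rests on three conditions. The variation is calculated from the recorded rest and Valsalva values. Individual ultrasound coefficients from the combined model are not interpreted; if they were shown, the report would need to say which two terms were fitted. And the conversion to mm uses a model of rest with age and BMI, which is how the section reads, although it does not name the model; the rest cut-off is not shown to be affected.
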